To support this interval, this study aims to produce data of the response in healthy volunteers to our ChAdOx-1 HBV vaccine following the use of the AZD1222 vaccine. T cell responses (the critical immunological factor in chronic HBV infection) will be compared in participants who have received either a prior two-dose series of AZD1222 with those who have received at least two prior doses of either the Pfizer mRNA COVID 19 vaccine (Comirnaty) or the Moderna COVID-19 vaccine (Spikevax). Due to the recommendation to use the AZD1222 in those over the age of 40 years, we will confine our study to 40-60 years of age and keep the interval from the latest COVID-19 vaccine to a narrow window of 10-18 weeks. No interference on HBV -focused T cell responses is expected from either the Pfizer vaccine or the Moderna vaccine, so the interval from the latest COVID-19 vaccine will be between 6 to 30 weeks

2

STUDY OBJECTIVES AND ENDPOINTS

Objectives	Endpoints
Primary	Primary
Determine the safety and tolerability of different doses of a single vaccination of ChAdOx1-HBV in healthy participants and in participants with CHB infection and virally suppressed with oral antiviral medication.	Incidence of safety and reactogenicity events: 
 • Adverse events and/or adverse events leading to study discontinuation • Serious adverse events • Grade ≥ 3 local and systemic reactions
Secondary	Secondary

 • Determine the immunogenicity of ChAdOx1-HBV in (A) healthy participants and in (B) participants with CHB, virally suppressed with oral antiviral medication 
Determine the effect of ChAdOx1-HBV on the level of HBsAg in participants with CHB infection, virally suppressed with oral antiviral medication
	
 • A multi-parameter index made of CD4+ magnitude, CD4+ avidity, and CD8+ magnitude • Mean reduction in HbsAg titre at Day 84 and Day 168 post-vaccination (last visit) • Proportion of CHB participants with HbeAg and HbsAg loss • Proportion of CHB participants with HbeAg and HbsAg seroconversion • Reduction of hepatitis B DNA levels • Total T cell response to the antigens encoded by ChAdOx1-HBV as measured in a peptide-stimulated ELISpot assay
Exploratory	Exploratory

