4.3.1.2 Study Discontinuation

Participants may choose to discontinue study assessments by withdrawal of consent. If the participant discontinues from taking the study vaccine but does not withdraw consent, the Investigator or research worker should attempt to continue safety follow-up assessments.

Participants may be withdrawn from the study vaccine, but followed up for safety, in the event of:

- A severe adverse event or SAE
- Difficulties in obtaining blood or other samples
- Failure of the participant to comply with the protocol requirements or to cooperate with the Investigator
- For safety reasons, it being in the best interest of the participant that he/she be withdrawn, in the Investigator's opinion
- A positive pregnancy test or if the participant is non-compliant with the contraception requirements (see [Section 4.2](#))
- Development of a medical condition that requires concomitant treatment with a potentially toxic therapy

Participants must be withdrawn from the study in the event of:

- Withdrawal of consent

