Unsolicited adverse events are other events meeting the criteria for adverse events (see [Section 8.2.1](#)) apart from those the participant is specifically asked about. Unsolicited

¹ In the event that they persist longer than 3 days then an adverse event will be recorded

non-serious adverse events will be collected from the date the informed consent is signed to 28 days post-vaccination. Hospitalisations, other SAEs and AESIs will be collected for the duration of the study.

Participants will collect unsolicited adverse events in the eDiary and these will be reviewed during clinic visits with the participant and relevant information (event term, start and end date, severity, causality, outcome and seriousness) collected and entered into the eCRF as described in [Section 8.2.3](#).

7.3.2 *Laboratory Safety Tests*

Laboratory safety tests will be performed at each of the timepoints according to [Table 2](#), as per [Sections 7.1.4.1](#) and [7.1.4.2](#). Extra laboratory safety tests may be performed if the Investigator deems them to be necessary to fully evaluate an adverse event. In the event that the Investigator elects to order non-protocol-specified laboratory tests, the Investigator must record the rationale for the tests and a determination of clinical significance of the result in the source documents. The Investigator must keep the local Medical Monitor informed of adverse events of clinical significance.

Abnormal results and findings will be discussed as applicable with the participant, and the participant will be referred for follow-up with their healthcare provider if necessary.

Results from the LFTs obtained on the study must be reviewed by the Investigator (or a designee who is a medically qualified study team member) and managed in accordance with the study centre procedures. The clinical significance of all results outside of the normal range will be determined by the Investigator and may be reported as an adverse event at the discretion of the Investigator.

7.3.3 *Physical Examination*

A skin, respiratory, cardiovascular, abdominal and lymphatic system examination will be performed at screening and pre-vaccination on Day 0. A symptom-directed physical examination will be performed at all other clinic visits if required. Results will be recorded as normal, abnormal and not clinically significant or abnormal and clinically significant.

7.3.4 *Vital Signs*

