The reporting period for all adverse events begins on the date the informed consent is signed. Solicited adverse events are recorded in the eDiary up to 3 days post-vaccination. All other events are recorded in the eCRF up until Day 28. All SAEs and or Adverse events of special interest are recorded until at least 168 days after the last study vaccination dose and for all serious or study vaccine-related adverse events until these are resolved or until participant contact discontinues.

Adverse event information will be collected at study visits and participant will be instructed to call study team members to report any abnormalities during the intervals between study visits and to come to the study centre if medical evaluation is needed and the urgency of the situation permits.

8.2.3 *Recording and Assessment of Adverse Events by the Investigator*

Solicited adverse events are recorded in the eDiary up to 3 days post-vaccination. All other adverse events are recorded in the eCRF up to until Day 28. All adverse events, both those observed by study team members and those spontaneously reported by the participant, will be recorded in the eCRF. Solicited adverse events will be reported using pre-defined terms. Unsolicited adverse events will be reported using a recognised medical term or diagnosis that accurately reflects the event.

Adverse events will be assessed by the Investigator, or a medically qualified study team member, for severity, relationship to study vaccine, action taken, outcome and whether the event meets criteria as an SAE according to the following guidelines:

8.2.3.1 *Assessment of Severity*

The severity of adverse events will be graded according to the toxicity table in [Appendix 1](#). The scale shown in [Table 3](#) will be used to assess severity of adverse events not listed in [Appendix 1](#).

Table 3 Severity Grading of Adverse Events not listed in the Toxicity Table for Clinical and Laboratory Abnormalities

Grade	Severity	
1	Mild	Asymptomatic or mild symptoms; clinical or diagnostic observations only; or intervention not indicated; no disruption of normal daily activity.
2	Moderate	Minimal, local, or non-invasive intervention indicated; discomfort sufficient to reduce or affect daily activity.
3	Severe	Severe or medically significant, but not immediately life-threatening; hospitalisation or prolongation of hospitalisation indicated; inability to work or perform normal daily activity.

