Every effort should be made by the Investigator to determine the existence of any pre-existing conditions (e.g. headache in adults or rashes in infants on study Day 0 with onset prior to study vaccination) that must be taken into consideration when assessing causal relationship of an adverse event. Pre-existing conditions should be recorded in the eCRF as baseline history and substantiated by appropriate source documentation. Intermittent conditions such as headaches in adults or irritability in infants may not be present on study Day 0 but may represent an adverse event if the intensity or duration of the event is worse than usual following study vaccine.

8.2.3.3 *Action Taken with Study Vaccine*

The action taken with the study vaccine will be recorded as None, as only one dose is given.

8.2.3.4 *Assessment of Outcome*

The outcome of the adverse event will be assessed as:

- Recovered/resolved
- Recovered/resolved with sequelae
- Not recovered/resolved
- Unknown
- Fatal

8.2.4 *Reporting Requirements and Procedures for Serious Adverse Events*

All SAEs are reported to the Sponsor for the entire study period. Suspected, unexpected, serious adverse reactions are reported even after the study is over, if the Sponsor, local Medical Monitor or Principal Investigator becomes aware of them. The study centre will be provided with specific reporting procedures including the SAE paper form and any supplemental reporting forms to be used. SAEs will be reported on the SAE paper form and the adverse event eCRF using a recognised medical term or diagnosis that accurately reflects the event.

SAEs will be assessed for severity, causal relationship to the study vaccine or alternative aetiology by the Sponsor and Investigator. The onset and resolution dates of the event and medical care taken in response to the event will be documented. If the event has not resolved by the end of the study is enrolled into, it will be documented as "ongoing" on the eCRF, however, follow-up of the SAE must continue until resolved or the condition has stabilised. Information recorded on the eCRF must be substantiated in the source documents.

The SAE form for that event must be completed by the Investigator, within 24 hours of the study centre becoming aware of the event. The SAE form should be completed with all information known at the time and scanned and emailed to the local Medical Monitor and to [REDACTED]

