14. TABLE AND LISTING SHELLS

Table 14.1.1
Disposition
All Participants

	Healthy Participants						CHB Participants						Healthy Participants								
	Low Dose (N=xx)			High Dose (N=xx)			Low Dose (N=xx)			High Dose (N=xx)			ChAdOx1 (N=xx)			mRNA (N=xx)			Covid-19 Vaccinated		
	n	(%)	n	n	(%)	n	n	(%)	n	n	(%)	n	(%)	n	(%)	n	(%)	n	(%)		
Screen Failure [1]	xx		xx	xx		xx	xx		xx	xx		xx	xx		xx	xx		xx	xx		
Vaccinated	xx		xx	xx		xx	xx		xx	xx		xx	xx		xx	xx		xx	xx		
Safety Analysis Set	xx	(xx,x)	xx	(xx,x)	xx	(xx,x)	xx	(xx,x)	xx	(xx,x)	xx	(xx,x)	xx	(xx,x)	xx	(xx,x)	xx	(xx,x)	(xx,x)		
[2]	xx	(xx,x)	xx	(xx,x)	xx	(xx,x)	xx	(xx,x)	xx	(xx,x)	xx	(xx,x)	xx	(xx,x)	xx	(xx,x)	xx	(xx,x)	(xx,x)		
PP Analysis Set [3]	xx	(xx,x)	xx	(xx,x)	xx	(xx,x)	xx	(xx,x)	xx	(xx,x)	xx	(xx,x)	xx	(xx,x)	xx	(xx,x)	xx	(xx,x)	(xx,x)		
Immunogenicity Analysis Set [4]	xx	(xx,x)	xx	(xx,x)	xx	(xx,x)	xx	(xx,x)	xx	(xx,x)	xx	(xx,x)	xx	(xx,x)	xx	(xx,x)	xx	(xx,x)	(xx,x)		
Completed Study [5]	xx	(xx,x)	xx	(xx,x)	xx	(xx,x)	xx	(xx,x)	xx	(xx,x)	xx	(xx,x)	xx	(xx,x)	xx	(xx,x)	xx	(xx,x)	(xx,x)		
Did not Complete Study	xx	(xx,x)	xx	(xx,x)	xx	(xx,x)	xx	(xx,x)	xx	(xx,x)	xx	(xx,x)	xx	(xx,x)	xx	(xx,x)	xx	(xx,x)	(xx,x)		
Reason for Withdrawal :																					
Reason 1	xx	(xx,x)	xx	(xx,x)	xx	(xx,x)	xx	(xx,x)	xx	(xx,x)	xx	(xx,x)	xx	(xx,x)	xx	(xx,x)	xx	(xx,x)	(xx,x)		
...	xx	(xx,x)	xx	(xx,x)	xx	(xx,x)	xx	(xx,x)	xx	(xx,x)	xx	(xx,x)	xx	(xx,x)	xx	(xx,x)	xx	(xx,x)	(xx,x)		

[1] Participants who were screened but not vaccinated with ChAdOx1-HBV.
 [2] Safety Analysis Set consists of all participants who received at least one vaccination. Data will be summarised according to the dose of vaccination actually received.

[3] Per Protocol (PP) Analysis Set consists of all participants in the safety analysis set who received the correct study vaccine and who had no major protocol deviations.

[4] Immunogenicity Analysis Set consists of all participants in the per-protocol set who have available immunogenicity data to evaluate the immunogenicity endpoints and did not have any major protocol deviations that would impact on the results of the immunological analysis.

[5] A participant completes the study by engaging in study activities up to and including the End of Study Visit at Day 168 (+/- 7 days).
 Percentages are based on the number of vaccinated participants.

All COVID-19 vaccinated participants were given the high dose of ChAdOx1-HBV vaccine.

Table 14.1.2
Demography
Safety Analysis Set

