To detect a Participant with an Adverse Event Leading to Withdrawal from the Study, use the study completion page where the Participant(s) withdrew from the study due to an adverse event.

Table 14.3.1.2
Treatment-Emergent Adverse Events by System Organ Class and Preferred Term
Safety Analysis Set

System Organ Class/ Preferred Term [1]	Healthy Participants			CHB Participants			Healthy Participants Covid-19 Vaccinated		
	Low Dose (N=xx)	High Dose (N=xx)	Low Dose (N=xx)	High Dose (N=xx)	ChAdOx1 (N=xx)	mRNA (N=xx)	High Dose (N=xx)	ChAdOx1 (N=xx)	mRNA (N=xx)
Number of Events	xx	xx	xx	xx	xx	xx	xx	xx	xx
Number of Participants with any adverse event	xx (xx,x)	xx (xx,x)	xx (xx,x)	xx (xx,x)	xx (xx,x)	xx (xx,x)	xx (xx,x)	xx (xx,x)	xx (xx,x)
System Organ Class 1									
Preferred Term 1	xx (xx,x)	xx (xx,x)	xx (xx,x)	xx (xx,x)	xx (xx,x)	xx (xx,x)	xx (xx,x)	xx (xx,x)	xx (xx,x)
Preferred Term 2	xx (xx,x)	xx (xx,x)	xx (xx,x)	xx (xx,x)	xx (xx,x)	xx (xx,x)	xx (xx,x)	xx (xx,x)	xx (xx,x)
System Organ Class 2									
Preferred Term 1	xx (xx,x)	xx (xx,x)	xx (xx,x)	xx (xx,x)	xx (xx,x)	xx (xx,x)	xx (xx,x)	xx (xx,x)	xx (xx,x)
Preferred Term 2	xx (xx,x)	xx (xx,x)	xx (xx,x)	xx (xx,x)	xx (xx,x)	xx (xx,x)	xx (xx,x)	xx (xx,x)	xx (xx,x)

Treatment-emergent events are those events with an onset on or after vaccination.
Table shows distinct number of participants with events for each system organ class/preferred term.
Percentages are based on the number of participants in the safety analysis set.
All COVID-19 vaccinated participants were given the high dose of ChAdOx1-HBV vaccine.

[1] MedDRA Version 22.1.

Programming Note(s):

Repeat table for treatment-emergent adverse events of special interest (table 14.3.1.3).
AESIs are flagged (as AESIs) on the study database.
Repeat table for Vaccine-related treatment-emergent adverse events (table 14.3.1.5).

Table 14.3.1.4
Treatment-Emergent Adverse Events by System Organ Class, Preferred Term and Severity
Safety Analysis Set

System Organ Class/ Preferred Term [1] / Severity	Healthy Participants		CHB Participants		Healthy Participants Covid-19 Vaccinated		Total (N=xx)
	Low Dose (N=xx)	High Dose (N=xx)	Low Dose (N=xx)	High Dose (N=xx)	ChAdOx1 (N=xx)	mRNA (N=xx)	
System Organ Class 1							
Grade 1	XX (XX.X)	XX (XX.X)	XX (XX.X)	XX (XX.X)	XX (XX.X)	XX (XX.X)	XX (XX.X)
Grade 2	XX (XX.X)	XX (XX.X)	XX (XX.X)	XX (XX.X)	XX (XX.X)	XX (XX.X)	XX (XX.X)
Grade 3	XX (XX.X)	XX (XX.X)	XX (XX.X)	XX (XX.X)	XX (XX.X)	XX (XX.X)	XX (XX.X)

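### A non-serious AE that starts after Day 28 and leads to study exit needs no AE record, so the withdrawal count and the AE outputs can disagree; the completion footnote also contradicts SAP 10.1.1

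*Protocol*

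**What the plan says.** **Endpoint.** The first bullet of the primary endpoint (Protocol 2, SAP 7.1) reads "Adverse events and/or adverse events leading to study discontinuation".

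**Recording window.** Protocol 7.3.1.2 states that "non-serious adverse events will be collected from the date the informed consent is signed to 28 days post-vaccination". Section 8.2.2 agrees: "All other events are recorded in the eCRF up until Day 28". Section 8.2.3 and Table 2 footnote [i] repeat the limit. Hospitalisations, SAEs and AESIs are collected for the whole study (7.3.1.2).

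**Leaving the study.** Protocol 4.3.1.2 has two lists. One begins "Participants may be withdrawn from the study vaccine, but followed up for safety, in the event of" and includes a severe AE or an SAE. The other begins "Participants must be withdrawn from the study in the event of" and has one entry, withdrawal of consent. Section 6.5 lets a participant leave at any time for any reason, foresees medical reasons, and has the reason documented in the eCRF. On the AE form, 8.2.3.3 says: "The action taken with the study vaccine will be recorded as None, as only one dose is given".

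**Analysis.** SAP 10.8.1 summarises participants with a TEAE leading to withdrawal and defines them as those who withdrew because of an AE. The programming note to Table 14.3.1.1 says to "use the study completion page where the Participant(s) withdrew from the study due to an adverse event". Listing 14.3.2.2 shows the term, coding, dates, severity, treatment emergence, seriousness, relatedness and outcome of each such event. Protocol 10.2.2.6.1 promises a narrative for every TEAE leading to study discontinuation.

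**Completion.** Table 14.1.1 footnote 5 has a participant complete by taking part "up to and including the End of Study Visit at Day 168 (+/- 7 days", with no mention of cohort. SAP 10.1.1 sets Day 168 for cohorts 1-4 and Day 84 for cohorts 5-6.

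**The concern.** The endpoint component covers the whole of follow-up, but routine recording of non-serious AEs stops at Day 28. The count and the event details come from two different forms, and neither document requires them to agree. If someone leaves late because of a non-serious event, the summary table can report an AE withdrawal that no AE table or listing explains. The reader of the report could not tell what the event was, how severe it was, or whether the investigator thought it vaccine-related. In a first-in-human study with cohorts of 5 or 6, one such exit would be examined closely.

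A second gap sits beside it. Neither document says whether a participant who withdraws consent because of an AE is entered as an AE withdrawal or as a consent withdrawal. The component depends on that choice.

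The footnote concerns the same disposition data. If it were programmed as written, completion in cohorts 5-6 would be reported wrongly.

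**Working it through.** The plan states no expected count or rate for this component, so there is no figure to reproduce. The check traces the rules and then does the day arithmetic.

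**1. What is still recorded if it starts after Day 28**
- SAEs, hospitalisations and AESIs, including non-serious AESIs: yes (7.3.1.2, 8.2.2).
- Non-serious events of concern believed related to vaccine or procedures: yes, through 8.2.6. The last sentence of 8.2.2 may also be read as covering vaccine-related events.
- Non-serious, non-AESI events not believed related: no requirement found.

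Events that started by Day 28 are followed up under 8.2.5.1 and are not affected.

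**2. One hypothetical case.** A cohort 3 participant has a non-serious, non-AESI event starting on Day 45, judged unrelated, and leaves because of it on Day 60.

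| Output | Source | Result |
|---|---|---|
| Table 14.3.1.1, AE leading to withdrawal | Completion page | Counted, if AE is given as the reason |
| Table 14.3.1.1, any AE; Tables 14.3.1.2 and 14.3.1.4 | AE record | This event absent |
| Listing 14.3.2.2 | AE record | No term, onset, grade or causality |
| Narrative (Protocol 10.2.2.6.1) | AE record plus source notes | No required grade or causality |

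If the participant had no other AE, one table would count them as leaving because of an AE and also as having had none. SAP 10.8.1 adds to the difficulty: it calls the item a TEAE, and treatment emergence is decided by onset date, which the completion page is not said to hold.

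**3. Length of the unrecorded period** (cohort sizes from SAP Table 1, visits from SAP 10.1.1)
- Cohorts 1-4: n = 5 + 5 + 6 + 6 = 22; (168 - 28)/168 = 140/168 = 83.3%.
- Cohorts 5-6: n = 15 + 15 = 30; (84 - 28)/84 = 56/84 = 66.7%.
- All: scheduled days 22 x 168 + 30 x 84 = 3,696 + 2,520 = 6,216; inside the window 52 x 28 = 1,456; 1,456/6,216 = 23.4%.

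These are shares of time, not of events.

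**4. Illustration with assumed inputs.** Let q be the risk of leaving because of an AE (2% to 10%) and s the share of late events needing no AE record (50% to 100%), with onset uniform over follow-up. None of these is in the documents.
- Expected AE exits = 52q, from 1.04 to 5.20.
- Exits without an AE record = s x q x (22 x 140/168 + 30 x 56/84) = s x q x 38.33.
- Lowest: 0.5 x 0.02 x 38.33 = 0.38. Highest: 1.0 x 0.10 x 38.33 = 3.83.
- Completion-page count: still 1.04 to 5.20, provided AE is given as the reason.

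So the Day 28 rule removes the details but leaves the count.

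**5. Footnote 5.** Cohorts 5-6 have their last visit at Day 84 and cannot reach Day 168. Taken literally, the footnote makes 30 of 52 participants (57.7%) non-completers even with perfect follow-up. SAP 10.1.1 makes them completers.

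**The case against.** Three stronger readings are tempting, and the documents do not support them.

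- **That only consent withdrawal can end participation.** The one-entry list in Protocol 4.3.1.2 says when a participant must be withdrawn; it does not list every way out. Section 6.5 allows exit for any reason, including a medical one, and records it. Keeping people with AEs in safety follow-up was a deliberate response to the regulator's assessment.
- **That the count is driven towards zero, or would read about 0 of 52.** The SAP uses the completion page, which has no Day 28 limit, and its programming note presupposes that AE can be given as a reason there. No rate is stated from which a near-zero count could be predicted.
- **That about 77% of the relevant events are lost.** That figure (1 - 1,456/6,216 = 76.6%) is person-time. Reading it as events needs uniform onset over up to 168 days after a single dose, which nothing in the documents supports.

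The defence also says that much is still captured after Day 28, and this is largely right. Its limit is that 8.2.6 covers only events believed related, whereas the endpoint has no such restriction. Section 8.2.3 also says all AEs go into the eCRF, but directly after repeating the Day 28 limit. Nor do the documents say that an AE-prompted consent withdrawal will be coded as consent; they leave it open. Section 8.2.3.3 concerns action on the vaccine, so it does not show that the eCRF lacks a field linking an AE to study exit. The eCRF is not among the documents.

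On footnote 5, SAP 10.1.1 is the governing definition, so the likeliest outcome is a wrong footnote rather than 30 misclassified people. That makes it editorial, but it is still a contradiction.

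**Conclusion.** The point holds as a traceability gap. A non-serious, non-AESI event that starts after Day 28, falls outside the related-event routes and causes exit can be counted as an AE withdrawal without a required AE record. Table 14.3.1.1 can then disagree with the TEAE tables and Listing 14.3.2.2, and the promised narrative lacks required inputs. How AE-prompted consent withdrawals enter the count is also undefined.

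The number of participants affected cannot be derived from the documents and may be none. One such case would be 1/5 = 20% or 1/6 = 16.7% of a cohort among cohorts 1-4. The conclusion assumes that sites apply the Day 28 limit as written and that no eCRF instruction outside these documents already requires the record. AEs to Day 28, SAEs and Grade 3 or higher reactions are unaffected.

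The footnote contradiction needs no assumption. Its effect runs from a wrong footnote to 30 of 52 participants misreported, depending on which text is programmed.

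**What to change.** 1. **Protocol 7.3.1.2, 8.2.2 and 8.2.3:** add that any AE given as a reason, or part of the reason, for leaving the study is entered as an AE with term, onset, grade and causality, whatever its start day or seriousness.
2. **SAP 10.8.1, Table 14.3.1.1 and Listing 14.3.2.2:** count every vaccinated participant whose documented reason for leaving includes an AE, AE-prompted consent withdrawals included. Link the completion page to the AE record and check that the table and listing agree before database lock.
3. **Table 14.1.1 footnote 5:** replace it with the SAP 10.1.1 definition, Day 168 for cohorts 1-4 and Day 84 for cohorts 5-6.

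The cost is a few sentences in each document and, if the eCRF has no such link, one field or comment on the completion page. Protocol 6.5 already asks sites to find out and document why a participant leaves. For participants who have already left, the documented reasons can be reviewed at the data review meeting and missing AE details queried. No visit, sample or treatment rule changes.
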